**Table 10-2: Exposure time at risk**

Exposure Category	Start Date	End Date	Duration of Exposure
Total BKZ exposure	First dose of BKZ in PA0008	Last dose of BKZ in PA0009	Minimum of (End date – start date + 140 a ) and (Date of last clinical contact b – start date + 1)
Total exposure to BKZ 160mgLD and 160mg	First dose of BKZ 160mgLD or 160mg in PA0008 or PA0009	Last dose of BKZ 160mg in PA0009	Minimum of (End date – start date + 140 a ) and (Date of last clinical contact b – start date + 1)
Exposure to BKZ 320mg	First dose of BKZ 320mg in PA0008	First dose of BKZ 160mg in PA0009 for subjects who were dosed in PA0009 c .  Last dose of BKZ 320mg in PA0008 for subjects who were not dosed in PA0009	(End date – start date + 1) for subjects who were dosed in PA0009.  Minimum of (End date – start date + 140 a ) and (Date of last clinical contact b – start date + 1) for subjects who were not dosed in PA0009.
Exposure to BKZ 160mg in PA0009	First dose of BKZ 160mg in PA0009	Last dose of BKZ 160mg in PA0009	Minimum of (End date – start date + 140 a ) and (Date of last clinical contact b – start date + 1)

**Table 10-2: Exposure time at risk**

Exposure Category	Start Date	End Date	Duration of Exposure
Subjects who died d	Start date for each option as above	Date of death	End date – start date + 1

BKZ=bimekizumab; LD=loading dose.

a 140 days refer to 5 half-lives of BKZ.

b Date of last clinical contact for each subject is defined as the maximum of [last visit date including SFU visit, last AE start date (including imputed AE start dates), date of study termination or completion, last date of study drug administration following rules for partial treatment end dates as per [Section 4.2.5](#)].

c In the event that the first dose in PA0009 was more than 140 days after the last dose in PA0008, the exposure time at risk for 320mg will be calculated using PA0008 end date – PA0008 start date + 140 days.

d For subjects who died, the date of death will be used to replace the end date in the calculation of exposure time at risk only if the subject died within the ‘at risk’ interval (ie, within 140 days following the last dose [not applicable for duration on BKZ 320mg]) or if the subject died before dosing in PA0009 (for time at risk on BKZ 320mg). If the subject died more than 140 days after the last dose of BKZ in PA0009 the exposure time at risk will be calculated using the ‘at risk’ interval of 140 days. Note that date of death should be equivalent to date of last clinical contact.

In the event that a subject received an incorrect (unplanned) treatment sequence the calculations for study medication duration and exposure time at risk will be adjusted accordingly following the principles outlined above and this will be documented in the relevant dataset specifications.

Three summaries of exposure will be provided: 2 for exposure in PA0009 and 1 for exposure in PA0008 and PA0009 combined:

- For the PA0009 summary, durations of exposure and times at risk will be summarized by treatment group at completion of PA0008 and overall. This summary will be repeated by SS Sub-population.
- For the PA0008 and PA0009 combined table, the duration of exposure and time at risk for ‘BKZ 160mg/BKZ 160mgLD combined’, ‘BKZ 320mg’ and ‘BKZ Total’ will be summarized. Subjects who took bimekizumab 320mg during PA0008 will contribute to all three columns. Subjects who did not take 320mg in PA0008 will contribute to the ‘BKZ 160mg/BKZ 160mgLD’ and ‘BKZ Total’ columns.

The total time at risk in years will be included in the exposure tables. This will be calculated by summing the time at risk across all subjects (per treatment group) and will be expressed in years and presented to 0 decimal place.

Start date of study medication in PA0008, start and end dates of study medication in PA0009, the durations of exposure and the times at risk will be listed.

## 10.2 Adverse events

An AE is any untoward medical occurrence in a patient or clinical investigation subject administered a pharmaceutical product that does not necessarily have a causal relationship with this treatment. An AE can therefore be any unfavorable and unintended sign (including an abnormal laboratory finding), symptom, or disease temporally associated with the use of a medicinal (investigational) product, whether or not related to the medicinal (investigational) product.

AEs that occurred during the PA0008 study and are ongoing at the time of enrolment (signed informed consent) in PA0009 will be captured in the PA0009 database and followed up until the AEs have resolved, have stable sequelae, the Investigator determines that it is no longer clinically significant, or the subject is lost to follow-up.

This follow-up requirement applies to AEs, SAEs, AEs of special interest (AESI), and AEs defined as Safety Topics of Interest; further details regarding follow-up of Potential Drug-induced Liver Injury (PDILI) events are provided in the protocol Section 9.5.1. Information on SAEs obtained after clinical database lock will be captured through the Patient Safety database without limitation of time.

If an AE is ongoing at the end of the PA0009 study, follow-up should be provided until resolution/stable level of sequelae is achieved, or until the Investigator no longer deems that it is clinically significant, or until the subject is lost to follow-up. If no follow-up is provided, the Investigator must provide a justification. The follow-up will usually be continued for 20 weeks after the subject has discontinued his/her IMP.

All AEs occurring during the PA0009 study (ie, after signature of the informed consent document) will be recorded in the eCRF. For each AE the following information will be recorded in the eCRF: AE term (verbatim term), date of onset, whether or not the AE was classified as a SAE, as an AESI, intensity, relationship to study medication, action taken with study medication, other action taken, outcome, date of outcome, and whether the AE led to study drug discontinuation or to study discontinuation.

The following code lists will be used for AE recording:

- Pattern of event: intermittent or continuous.
- Intensity of event: mild, moderate or severe.
- Relationship: related or not related.
- Action taken with IMP: dose not changed, dose reduced, dose increased, drug temporarily, interrupted, drug permanently withdrawn or not applicable.
- Outcome: resolving, not resolved, resolved, resolved with sequelae, worsened, fatal or unknown.

AEs (including SAEs) are characterized as either non-treatment-emergent or treatment emergent according to the following criteria:

- Non-treatment emergent AEs are those with onset date after a 140-day period after the end date of study medication.
  - Any AE occurring more than 140 days after the last administration of study medication in PA0008 and prior to the first administration of study medication in PA0009 will also be considered as non-treatment emergent, and will therefore be excluded from the summary tables. Such events will be included in the listings.
- TEAEs are those with onset date on or after the start date of study medication in PA0009.
- Events that were ongoing at the end of PA0008 will have their treatment-emergent status taken from the PA0008 database.

For all AEs the following variables will be calculated (see [Section 10.2.1](#)):

- Duration.
- Time since first bimekizumab dose.
- Time since last/latest bimekizumab dose.

AE summaries will, in general, include only events with onset on or after the start date of study treatment in PA0009. Certain displays will be repeated including all AEs in PA0008 (with the exception of those with onset during placebo treatment) and PA0009 as outlined below. These displays will include only subjects from PA0008 who were enrolled in PA0009.

In general, the attributes of these events (for AEs that started and were resolved in PA0008) will be taken from the PA0008 database. However, the identification of Safety Topics of Interest will be made across all events in PA0008 and PA0009 using the criteria defined in this SAP.

For events which were ongoing at the end of PA0008, the following rules will be implemented:

- Onset date (and derived variables) will be taken from the PA0008 database
- End date, outcome, actions taken and seriousness will be taken from the PA0009 database.
- In order to ensure that AEs are not duplicated in the outputs these will be merged across the studies by Subject ID, verbatim term (AETERM), dictionary-derived term (AEDECOD), start date (AESTDTC), relationship (AEREL) and severity (AESEV) to create one record for the specific event.

Summaries of AEs in PA0008 and PA0009 combined will include AEs with onset on the first dose of bimekizumab in PA0008 up to 140 days after the last dose of bimekizumab in PA0009. AEs which occur on the day of a treatment switch will be considered to have begun on the previous treatment, with the exception of the following AEs which will be considered to have begun on the new treatment:

- Events that fulfill the anaphylaxis criteria for acute events (see [Section 10.2.3](#)).
- Events that fulfill the hypersensitivity reaction criteria for (see [Section 10.2.3](#)).
- Events with a HLT of “Administration site reactions NEC”.
- Events with an HLT of “Injection site reactions”.

AEs that occur on the first day of bimekizumab treatment in PA0008 following initial treatment with placebo will not be included in the summaries, unless they fulfill 1 of the 4 exception criteria above. AEs that occur after the last dose of bimekizumab in PA0009 and up to 140 days after the last dose of bimekizumab in PA0009 will be assigned to bimekizumab 160mg.

AEs will be presented as “number of subjects (percentage of subjects) [number of events]”. “[number of events]” will include all cases of an AE including repeat occurrences in individual subjects, while “number of subjects” will count each subject only once.

An overview of TEAE (number and percentage of subjects with any TEAE, serious TEAE, TEAE leading to study discontinuation, TEAE leading to permanent withdrawal of study medication, drug-related TEAE, severe TEAE, fatal AE [see note below], fatal TEAE and TEAE

with missing seriousness) will be provided by treatment group at completion of PA0008 and overall. This summary will be repeated by SS Sub-population.

This table will be repeated including all TEAEs in PA0008 and PA0009 reported for subjects in the PA0009 SS (with the exception of those with onset during placebo treatment) combined. The 'BKZ 160mg' treatment column in this table will include subjects in both the BKZ 160mgLD and BKZ 160mg treatment groups.

The category for fatal AEs will be based on all subjects enrolled in PA0009 in all the above summaries.

The following categories of TEAE will be summarized by MedDRA SOC, HLT and PT including EAIR and EAER (calculated as described in [Section 10.2.2](#)), where all summaries refer to AEs reported in PA0009 only except where stated:

- All TEAEs by treatment group at completion of PA0008 and overall.
- All TEAEs by treatment group at completion of PA0008 and overall, by SS Sub-population.
- Serious TEAEs by treatment group at completion of PA0008 and overall.
- Serious TEAEs by treatment group at completion of PA0008 and overall, by SS Sub-population.
- All TEAEs in PA0008 and PA0009 by treatment at time of AE onset (BKZ 160mg, BKZ 320mg and BKZ Total).
  - The 'BKZ 160mg' treatment column in this table will include subjects in both the BKZ 160mgLD and BKZ 160mg treatment groups.
- Serious TEAEs in PA0008 and PA0009 by treatment at time of AE onset (BKZ 160mg, BKZ 320mg and BKZ Total).
  - The 'BKZ 160mg' treatment column in this table will include subjects in both the BKZ 160mgLD and BKZ 160mg treatment groups.
- All TEAEs by timing of onset relative to ADAb status in PA0009. This will include columns for the following (regardless of PA0008 Baseline ADAb status):
  - TEAEs starting before the first ADAb positive result in PA0009 including the PA0009 EV (includes ADAb Categories 2a, 4a and 5a).
  - TEAEs starting on the same date or after the first ADAb positive result in PA0009 including the PA0009 EV (includes ADAb Categories 2a, 4a and 5a).
  - TEAEs for subjects who are ADAb negative at all time points in PA0009 including the PA0009 EV (includes ADAb Categories 1a and 3a).

The following categories of TEAE will be summarized by MedDRA SOC, HLT, and PT, by treatment group at completion of PA0008 and overall:

- TEAEs leading to study discontinuation and/or permanent withdrawal of study medication.
- TEAEs leading to permanent withdrawal of study medication.
- TEAEs with a fatal outcome.

- All TEAEs by maximum relationship.
- Serious TEAEs by maximum relationship.
- TEAEs with a fatal outcome by maximum relationship.
- All TEAEs by maximum intensity.
- Non-serious TEAEs reported by more than the reporting threshold of 5% of subjects. The cut-off will be applied before rounding on each treatment group and overall.

A further summary will be presented by treatment group at completion of PA0008 and overall displaying the frequency of TEAEs by descending frequency of PT.

An additional table will be presented by MedDRA SOC, HLT and PT, by treatment at time of AE onset (BKZ 160mg, BKZ 320mg and BKZ Total) for all TEAEs in PA0009 and all TEAEs that were ongoing from PA0008 at the time of the PA0009 EV. Ongoing TEAEs are defined as TEAEs that started prior to the PA0009 EV and continued after the first dose of study medication in PA0009. The 'BKZ 160mg' treatment column in this table will include subjects in both the BKZ 160mgLD and BKZ 160mg treatment groups.

TEAEs classified as Safety Topics of Interest and associated tables are defined in [Section 10.2.3](#).

The following AE listings will be provided based on the ES:

- Glossary table for all AEs (this listing will include all events in PA0008 and PA0009 for subjects that were enrolled in PA0009 [with the exception of AEs with onset during placebo treatment]).
- All AEs (this listing will include all events in PA0008 and PA0009 for subjects that were enrolled in PA0009 [with the exception of AEs with onset during placebo treatment]).
- All SAEs (this listing will include all events in PA0008 and PA0009 for subjects that were enrolled in PA0009 [with the exception of AEs with onset during placebo treatment]).
- All AEs leading to study discontinuation.
- All deaths.

The following listings will be provided based on the SS:

- Serious infections TEAEs.
- Fungal infectious disorder TEAEs.
- Opportunistic infection (including tuberculosis) TEAEs.
- Malignant or unspecified tumor TEAEs.
- Malignant tumor TEAEs.
- Adjudicated cardiovascular TEAEs by event type.
- Adjudicated cardiovascular TEAEs by event type for major adverse cardiac events (MACE)
- Adjudicated cardiovascular TEAEs by event type for extended MACE
- TEAEs identified for potential review by the Cardiovascular Event Adjudication Committee.

- Neutropenia TEAEs.
- Suicidal ideation and behavior TEAEs.
- TEAEs identified for potential review by the Neuropsychiatric Adjudication Committee.
- TEAEs adjudicated by the Neuropsychiatric Adjudication Committee.
- Inflammatory bowel disease TEAEs.
- Hypersensitivity reaction TEAEs.
- Anaphylactic reaction TEAEs.
- Hepatic events TEAEs.
- Hospitalization/Emergency Room Visits.

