#### 2.2.1.2 Secondary safety variables

The secondary safety variable is the withdrawal due to TEAEs. This is measured by the incidence of TEAEs leading to study discontinuation and/or permanent withdrawal of study medication.

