### **5 STUDY POPULATION CHARACTERISTICS**

#### **5.1 Subject disposition**

Subject disposition (date of first and last subject visit, number of subjects included in each analysis set [ES, SS, and FAS]) will be presented overall, by region and for each site, and by treatment group at completion of PA0008 and overall for the ES.

The number and percentage of subjects in each analysis set (ES, SS and SS Sub-populations, and FAS) will be presented by treatment group at completion of PA0008 and overall.

The number and percentage of subjects who started, completed and discontinued the study, along with the primary reason for discontinuation will be presented by treatment group at completion of PA0008 and overall for the SS (a subject will be considered to have completed the study if they attended Visit 13 [Week 104]). For the purposes of the summaries the data will be taken directly from the eCRF page for study termination.

The number and percentage of subjects who started, completed and discontinued study medication, along with the primary reason for medication discontinuation will be presented by treatment group at completion of PA0008 and overall for the SS (a subject will be considered to have completed study treatment if they received a dose at Visit 12 [Week 100]). For the purposes of the summaries the data will be taken directly from the eCRF page for study medication discontinuation.

For any subjects where the data on the study termination and study medication discontinuation eCRF pages are inconsistent, the data reported on the study termination page will be considered

as primary ie, if a subject is reported as discontinuing from the study, they will be regarded as discontinuing study medication as well (regardless of whether this is reported in the eCRF).

Discontinuations due to AEs will be summarized by treatment group at completion of PA0008 and overall for the SS.

Subjects who did not meet the eligibility criteria and the inclusion and/or exclusion criteria not met will be listed for the ES.

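### The PA0009-only tables of withdrawal due to TEAEs leave out a subject withdrawn for an unchanged event carried over from bimekizumab treatment in PA0008

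*SAP*

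**What the plan says.** Protocol 4.2.1 names one secondary safety variable, withdrawal because of TEAEs, and sets no condition on when the event began. SAP 2.2.1.2 makes it operational: "This is measured by the incidence of TEAEs leading to study discontinuation and/or permanent withdrawal of study medication".

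SAP 10.2 contains the rules that decide which events reach the tables:

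- Definition of treatment-emergent: "TEAEs are those with onset date on or after the start date of study medication in PA0009".
- Events carried over from the lead-in study: "Events that were ongoing at the end of PA0008 will have their treatment-emergent status taken from the PA0008 database".
- Later attributes of those carried-over events: "End date, outcome, actions taken and seriousness will be taken from the PA0009 database".
- Default selection for summaries: "AE summaries will, in general, include only events with onset on or after the start date of study treatment in PA0009".
- Exception to the default: "Certain displays will be repeated including all AEs in PA0008 (with the exception of those with onset during placebo treatment) and PA0009 as outlined below".

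Two kinds of display in SAP 10.2 carry the variable. The first is the pair of tables by system organ class, high level term and preferred term, one for "TEAEs leading to study discontinuation and/or permanent withdrawal of study medication" and one for permanent withdrawal alone. No repeat with PA0008 events is listed for either. The second is the TEAE overview, which has one row for study discontinuation and another for permanent drug withdrawal. It is repeated with bimekizumab-period events from PA0008.

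Separately, SAP 5.1 says: "Discontinuations due to AEs will be summarized by treatment group at completion of PA0008 and overall for the SS". No onset condition is attached there.

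**The concern.** The rules for carried-over events only make sense if the sponsor expects such an event to lead to something in PA0009, such as stopping the drug. Status is inherited from PA0008 and the action is read from PA0009, so a withdrawal in the extension attaches to an event with an earlier onset. The default onset filter then removes that event from the one general table that matches the composite in SAP 2.2.1.2.

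The primary variables are treated differently. All TEAEs and serious TEAEs each get a combined PA0008 and PA0009 table by MedDRA term, and a further table shows PA0009 TEAEs together with those ongoing at entry. The withdrawal tables have no such counterpart, and that further table does not separate events that led to withdrawal.

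At stake is a possible undercount in a named secondary safety variable of a long-term safety study. There is also room for two programmers to reach different counts, because SAP 10.2 defines TEAEs by PA0009 onset and then lets earlier events keep treatment-emergent status.

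**Working it through.** **Reproducing a planned figure.** There is none. SAP 2.4 states that no formal sample size calculation was made, and neither document gives an expected withdrawal rate. The check is therefore to trace the rules, followed by a simple proportion.

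**Inputs.** The selection rules are those of SAP 10.2 quoted above. The worsening rule is protocol 9.1.7, under which an increase in intensity is reported as a repeat event with its own start date. The maximum N of 200 is from SAP 2.4. I read the actions taken from PA0009 as including the record that the event led to drug or study discontinuation. SAP 10.2 lists that as a separate item, so this reading is an assumption.

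**Tracing a test subject.** An event starts on bimekizumab in PA0008, is ongoing at entry, and leads to permanent withdrawal of drug in PA0009. In case A its intensity never rises. In case B it rises in PA0009 before the withdrawal, and the repeat record carries the action.

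| Display | Case A | Case B |
|---|---|---|
| Withdrawal tables by MedDRA term | not counted | counted |
| PA0009-only overview | not counted | counted |
| Combined PA0008 and PA0009 overview | counted | counted |
| Disposition, discontinuation due to AE | counted if that is the recorded reason | same |

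Case B passes because the repeat has a PA0009 start date. The merge key in SAP 10.2 includes both start date and severity, so the repeat is not folded back into the PA0008 record. Only case A is a gap.

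**What the combined overview does not supply.** It has no breakdown by MedDRA term. It shows the two withdrawal rows separately, not the composite. Its columns are BKZ 160mg, BKZ 320mg and BKZ Total by treatment period (SAP 3.7), so an event that began on 320mg and led to withdrawal on 160mg falls under 320mg and the total.

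**Size.** With k subjects missed out of N, the shift in percentage points is 100 × k / N.

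- One subject: 100 × 1/200 = 0.50. At an assumed N of 180 it is 0.56, and at an assumed N of 150 it is 0.67.
- Illustration, assuming 10 withdrawals with PA0009 onset among 200: 10/200 = 5.0%. Adding 1, 2 or 4 carried-over cases gives 11/200 = 5.5%, 12/200 = 6.0% or 14/200 = 7.0%.
- With k = 0 nothing changes.

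The base count of 10 and every k are assumptions. The shift per subject is larger within each treatment column, whose denominator is smaller; the documents do not give the split.

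**The case against.** The strongest reply is that the filter is a stated default with a stated exception, and that an incidence based on onset in the extension is a coherent convention. Much of this stands.

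- A reader might infer that these withdrawals vanish from every output. They do not. The combined overview counts them, disposition has no onset filter, SAP 5.1 lists study and treatment discontinuation reasons, and SAP 10.2 lists all AEs leading to study discontinuation.
- A reader might infer that slowly worsening events are missed. The documents do not support that where recorded intensity rises, because protocol 9.1.7 creates a new record that passes the filter.
- A reader might extend the point to deaths. The overview's fatal AE row is based on everyone enrolled, and all deaths are listed, so those events are already covered.
- A reader might call the likely mismatch with disposition an error. Disposition is taken from the eCRF termination and discontinuation pages, not from the action on the AE record, so exact agreement was never assured.
- Protocol 6.1 and 6.2 narrow the pool. Subjects must complete PA0008 without meeting a withdrawal criterion, and an ongoing SAE requires consultation with the Medical Monitor before entry.

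The convention argument does not fully answer the point. The SAP itself keeps treatment-emergent status for carried-over events, and SAP 2.2.1.2 counts TEAEs that lead to withdrawal without restricting onset. Under those two rules a case A subject belongs in the variable.

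**Conclusion.** The point holds in a narrow form. The PA0009-only displays of the secondary safety variable omit a subject withdrawn in PA0009 for a bimekizumab treatment-emergent event that began in PA0008 and was carried over without an increase in intensity. The combined overview is a partial remedy, for the reasons shown in the working.

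The effect is 0.5 percentage points per affected subject at N = 200. The documents give no count, which may be zero, and they support no estimate of the share of withdrawals caused by PA0008-onset events. The conclusion rests on applying the default filter to the withdrawal tables, for which SAP 10.2 lists no exception, and on the reading of actions taken stated above. It is worth correcting because the variable is a named secondary one and the correction is cheap, not because a large bias has been shown.

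**What to change.** In SAP 10.2:

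1. State which display reports the secondary safety variable.
2. Extend the two tables by MedDRA term (the composite of discontinuation and/or withdrawal, and permanent withdrawal alone) to include bimekizumab TEAEs ongoing from PA0008 whose PA0009 record shows that action. Say explicitly that the record of study discontinuation is also read from PA0009.
3. Add rows that split the count by onset in PA0008 and onset in PA0009, so that the PA0009-onset figure stays visible.
4. Add a footnote that events with onset on placebo remain excluded and that disposition uses the eCRF reason, so the two need not agree.

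The fatal-outcome table need not be redefined.

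The cost is some wording and one selection condition on records the SAP already merges and already identifies as ongoing. These tables carry no exposure-adjusted rates, so no person-time has to be recalculated. The reported incidence may become slightly less favourable.

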6.2 Exclusion criteria

Subjects are not permitted to enroll in the study if any of the following criteria are met:

1. Female subjects who plan to become pregnant during the study or within 20 weeks following last dose of study medication. Male subjects who are planning a partner pregnancy during the study or within 20 weeks following the last dose.
2. Subjects with any current sign or symptom that may indicate a medically significant active infection (except for the common cold) or has had an infection requiring systemic antibiotics within 2 weeks of study entry. The medical monitor must be consulted prior to subject's entry into PA0009 in such cases.
3. Subjects who meet any withdrawal criteria in PA0008. For any subject with an ongoing SAE, or a history of serious infections (including hospitalizations) in the lead-in study, the Medical Monitor must be consulted prior to the subject's entry into PA0009.

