- If only the year of the AE start date is specified, and the year of the start date of study medication in PA0009 is the same as the year of the AE start date, then use the start date of study medication in PA0009 (regardless of treatment switching). If this results in a start date after a known end date use the 1st of January of the year of the AE start date.
- If only the year and day of the AE start date are specified, and the year of the start date of study medication in PA0009 is not the same as the year of the AE start date, then use January of the year of the AE start date together with the known day.
- If only the year and day of the AE start date are specified, and the year of the start date of study medication in PA0009 is the same as the year of the AE start date, then use the start month of study medication in PA0009 together with the known day.

- If this results in a start date after a known end date use January of the year of the AE start date together with the known day.
- If this results in a start date prior to the start date of study medication in PA0009 (in the imputed month) the event will be considered to be treatment-emergent.
- If the AE start date is completely unknown and the AE stop date is unknown or not prior to the start date of study medication in PA0009, then use the start date of study medication in PA0009.

Imputation of partial AE stop date:

- If only the month and year of the AE stop date are specified, then use the last day of that month and that year.
- If only the day and year are specified, then use December of that year
- If only the year of the AE stop date is specified, then use December 31st of that year.
- If the AE stop date is completely unknown, do not impute the stop date.

In the event of ambiguity or incomplete data which makes it impossible to determine whether the AE was treatment-emergent, the AE will be considered treatment-emergent. For subjects who may have died during the study, imputed dates will be truncated at the date of death.

If the intensity of an AE is unknown, it is considered as severe. If the relationship to study drug is missing, it is considered as related.

If the seriousness of an AE is unknown, no imputation will be performed. Such events will therefore be excluded from any listings or summaries of SAEs.

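### Seriousness of events carried over from PA0008 is read only from PA0009, so a discordant or blank record would drop out of the combined serious-TEAE outputs and the SAE listing

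*SAP*

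**What the plan says.** SAP 10.2 treats PA0008 events in two ways.

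- Events that began and ended in PA0008: "In general, the attributes of these events (for AEs that started and were resolved in PA0008) will be taken from the PA0008 database".
- Events ongoing at the end of PA0008: onset date and treatment-emergent status come from PA0008, but "End date, outcome, actions taken and seriousness will be taken from the PA0009 database". The two records are then merged on subject, verbatim term, dictionary term, "start date (AESTDTC), relationship (AEREL) and severity (AESEV) to create one record for the specific event". Seriousness is not a merge key.

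SAP 4.2.3 makes no imputation where seriousness is unknown: "Such events will therefore be excluded from any listings or summaries of SAEs".

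Three outputs use the result:

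- The combined TEAE overview, which has a serious-TEAE row: "This table will be repeated including all TEAEs in PA0008 and PA0009 reported for subjects in the PA0009 SS".
- The combined table by system organ class, high level term and preferred term, with exposure-adjusted rates: "Serious TEAEs in PA0008 and PA0009 by treatment at time of AE onset (BKZ 160mg, BKZ 320mg and BKZ Total".
- The SAE listing: "All SAEs (this listing will include all events in PA0008 and PA0009 for subjects that were enrolled in PA0009".

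Protocol 6.2 foresees the situation. It requires Medical Monitor consultation before entry: "For any subject with an ongoing SAE, or a history of serious infections".

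**The concern.** Onset date, end date and outcome each have one natural source. Seriousness does not. Under Protocol 9.2.1 an event is serious once it meets any one criterion, such as hospitalization, and it does not cease to be an SAE when that phase ends. The combined tables are meant to count serious events on bimekizumab from the first dose in PA0008, yet the rule lets a later non-serious or empty field replace a positive value already held.

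This also departs from the SAP's own habits. SAP 4.2.3 treats unknown intensity as severe, missing relationship as related and ambiguous timing as treatment-emergent, and it uses PA0008 for missing start dates of PA0008 events.

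Blank fields are conceivable. Protocol 9.1.1 has ongoing PA0008 events captured in the PA0009 database, while Protocol 8.1 lists the recording of AEs among the entry items taken at PA0008 Week 48 that need not go on the PA0009 eCRF.

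**Working it through.** The plan gives no figure to reproduce. The check is to run every pair of seriousness values through SAP 10.2 and 4.2.3 and compare the result with a rule that counts an event as serious if either study says so.

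| PA0008 | PA0009 | In serious-TEAE outputs and SAE listing under the SAP | Serious in either study | Result |
|---|---|---|---|---|
| yes | yes | yes | yes | kept |
| yes | no | no | yes | lost |
| yes | blank | no (shown in missing-seriousness row) | yes | lost |
| no | yes | yes | yes | kept |
| no | no | no | no | same |
| no | blank | no (shown in missing-seriousness row) | no | same |
| blank | yes | yes | yes | kept |
| blank | no | no | no | same |
| blank | blank | no (shown in missing-seriousness row) | no | same |

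Five of the nine pairs are serious in at least one study. The SAP keeps three and loses two.

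**Which columns.** The combined tables assign events to the treatment at onset (SAP 10.2). A carried-over event began before PA0009 dosing, and 320mg was given only in PA0008 (SAP 3.7). A loss therefore falls on a PA0008 dose period, never on PA0009 160mg time. Events with onset on placebo are outside these tables anyway.

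**Size per lost event (illustration).** Assume the maximum of 200 subjects, all on bimekizumab from PA0008 Week 0 and followed for 48 + 100 + 20 = 168 weeks:

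- Time at risk = 200 × 168 × 7 / 365.25 = 643.9 subject-years. If all began bimekizumab at PA0008 Week 12: 200 × 156 × 7 / 365.25 = 597.9.
- Incidence lost per subject whose only serious event drops out = 1 / 200 = 0.5 percentage points.
- Crude rate lost = 100 / 643.9 = 0.16 per 100 subject-years (100 / 597.9 = 0.17).

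With assumed counts of subjects with a serious event, the 643.9 denominator and the exact Poisson interval of SAP 10.2.2:

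| Assumed true count | None lost | 1 lost | 3 lost |
|---|---|---|---|
| 20 | 3.11 (1.90 to 4.80) | 2.95 (1.78 to 4.61) | 2.64 (1.54 to 4.23) |
| 10 | 1.55 (0.74 to 2.86) | 1.40 (0.64 to 2.65) | 1.09 (0.44 to 2.24) |

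These rates are crude: the SAP's incidence rate stops the clock at first onset, so its denominator is somewhat smaller. A lost event weighs more in the 320mg column, where a subject contributes at most 48 weeks rather than 168. The documents do not give the number of subjects in that column.

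**How many records are exposed.** The documents do not say. If 5 to 10% of 200 subjects had an SAE in PA0008 (10 to 20) and 10 to 30% of those were ongoing at entry, 1 to 6 would be exposed to the rule. Both percentages are assumptions. The number lost is that figure times an unknown probability of discordance, which may be zero.

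**The case against.** The strongest reply is that the loss needs a recording discrepancy. The eCRF asks whether the AE was classified as serious, not whether its current phase is; the carried-over record is the same event followed to resolution; and any ongoing SAE at entry goes to the Medical Monitor. A serious event re-entered as non-serious would be an error, and Protocol 9.1.11 and 12.3.1 provide for SAE and database reconciliation. This stands as a limit on likelihood. Neither section calls for comparing the PA0008 and PA0009 flags, so it does not close the gap.

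Taking the later record also has merit, because it captures an event that becomes serious after rollover. That stands too, and an either-database rule keeps it. What such a rule gives up is the automatic effect of a legitimate later downgrade.

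A reader might infer that the loss would be invisible. The documents do not support that. The event stays in the combined all-TEAE table and the all-AE listing, and a blank is counted in the overview's missing-seriousness row. Only a yes/no conflict is flagged in no summary.

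If relationship or severity differs between the studies, the records do not match on the merge keys. The SAP does not say what follows, and the result could be a duplicate rather than a loss.

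**Conclusion.** The gap is real on the text, conditional in effect and limited in reach. SAP 10.2 has no PA0008 fallback for seriousness, so an event that is yes/no or yes/blank across the two studies leaves the combined serious-TEAE outputs and the all-SAE listing. If that happens, the cost is about 0.5 percentage points and 0.16 per 100 subject-years in the Total column for each subject whose only serious event is lost, under the assumptions shown above.

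Two stronger readings are not supported. One is that 1 to 6 SAEs will be lost: that range is an assumed number exposed to the rule, and no discordant record is shown to exist. The other is that the study's primary serious-TEAE result is biased: the PA0009-only tables count events with onset on or after PA0009 dosing and are untouched. The combined summaries are not among the analyses in Protocol 13.3.1 and were added by SAP Amendment 1. The point is low priority, but worth correcting because serious events may be few and the remedy is cheap.

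**What to change.** In SAP 10.2, take seriousness out of the list of attributes read from PA0009 and add: *Seriousness is Yes if the event is serious in either the PA0008 or the PA0009 database; if missing in PA0009, the PA0008 value is used.* Keep end date, outcome and actions taken from PA0009. Before database lock, list carried-over events whose seriousness differs between the studies, so that a genuine reclassification can be documented.

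The cost is one sentence in the SAP, one line in the merge program and one short listing. The two lost pairs are restored and no other pair changes its SAE status; a no/blank event would move from missing to non-serious. The downsides are a possibly slightly higher SAE count, and that a legitimate later downgrade would not automatically override PA0008. The listing is there to handle the latter.
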